4.4. Treatments

4.4.1. Treatments Administered

Zoliflodacin is a spiropyrimidinetrione antibacterial agent, with a novel mode of action. It is a first-in-class oral gyrase inhibitor being developed for treatment of uncomplicated gonococcal infection, including cases caused by isolates with resistance to currently available treatments. A single oral dose of zoliflodacin has been shown to be effective against uncomplicated gonorrhea caused by *N. gonorrhoeae* strains susceptible or resistant to currently available therapies. These findings supported the ongoing clinical development of zoliflodacin as a potential new therapeutic option for uncomplicated gonorrhea.

4.4.2. Identity of Investigational Product(s)

Zoliflodacin is presented as granules for oral suspension, 50 % wt/wt, packaged in a single sachet. Each sachet contains 2 g of spray-dried zoliflodacin, co-formulated with [REDACTED].

4.4.3. Method of Assigning Subjects to Treatment Groups (Randomization)

This is a single arm trial. All subjects will receive a single 4 g oral dose of zoliflodacin.

4.4.4. Selection of Doses in the Study

Single zoliflodacin doses ranging from 200 mg to 4 g were generally safe and well tolerated in the Phase 1 and Phase 2 clinical trials conducted to date in healthy subjects and patients with uncomplicated gonorrhea.^{1,2,3} The current trial will further characterize the PK and safety profiles of the 4-g dose of a new zoliflodacin formulation. This dose could result in drug exposures that are multiples of the proposed 2-g therapeutic dose and meet the requirements for a supratherapeutic dose according to the ICH/FDA E14 Guidance for thorough QTc studies.⁴

4.4.5. Selection and Timing of Dose for Each Subject

Eligible subjects will receive a single 4-g dose (2 sachets of 2 g of zoliflodacin reconstituted on the same day and administered in a total of [REDACTED]) orally after an overnight fast. After the [REDACTED] of zoliflodacin is administered, an additional [REDACTED] will be added to the same cup and consumed by the subject to chase the initial dose. Ingestion of the content of both the initial [REDACTED] volume and the [REDACTED] should be completed within 5 min. After dosing, subjects will continue to fast for an additional 4 h while water is allowed *ad lib*. All subjects will receive zoliflodacin in the morning of Day 1 in a staggered fashion several minutes apart.

4.4.6. Blinding

This is an open-label study, no blinding procedures are required.

4.4.7. Prior and Concomitant Therapy

Concomitant medications include the following: prescription drugs, birth control hormonal preparations, non-prescription medication, herbs, vitamins, nutritional supplements, and illicit and recreational substances. Any of these taken before or after dosing will be reported as Prior Medications or Concomitant Medications, respectively.

Prior prescription medication information will be recorded at Screening Visit and, except for hormonal contraceptives, should not be taken for 30 days before dosing or during the study period.

Zoliflodacin should not be co-administered in subjects using strong (i.e., avasimibe, carbamazepine, phenytoin, rifampin, and St. John's wort) or moderate (i.e. efavirenz, bosentan, etravirine, modafinil, and nafcillin) inducers of CYP3A4. These drugs should not be taken for 30 days before dosing and during the study period.

A vaccine should not be received within 30 days before dosing or before the end of the trial, except for licensed influenza vaccine during the flu season, which may be administered up to 7 days before or after dosing.

Non-prescription medications, herbs, vitamins, and nutritional supplements should not be taken within 15 days before dosing. OTC medications taken for a brief period (<48 h) for the treatment of common symptoms (such as headache, indigestion, muscle pain) may be allowed as approved by the designated study clinician.

Allowed medications include: oral contraceptives; H1 antihistamines; topical/ intranasal corticosteroids; nonsteroidal anti-inflammatory drugs (NSAIDS); licensed influenza vaccine during the flu season, 7 days before or after dosing.

Blood/blood products (RBCs, WBCs, platelets, and plasma) should not be donated within 60 days of dosing or received before Final Visit.

Following dosing, each new concomitant medication and changes to existing medications will be recorded. Subjects will be required not to utilize non-study medication during the trial except those deemed necessary by the Site PI or sub-investigator.

Any drug (e.g., non-prescription medications, herbal supplements, vitamins, or prescription medications) or vaccine or blood/blood products used by the subject during the trial will be recorded in the subject's source documents and on the appropriate electronic case report form (eCRF), and the PI or authorized study clinician (listed on FDA Form 1572) will note whether the use was medically indicated and immediately necessary. Any use of medications not authorized by the study PI or authorized clinician will be recorded as a deviation.

4.4.8. Treatment Compliance

All subjects will receive a single 4 g dose of zoliflodacin administered in the clinic. Dates and times of administration will be recorded by site personnel. Complete information regarding any partial or interrupted dosing will be documented.

4.5. Efficacy and Safety Variables

As this study is a Phase I clinical trial in healthy adult subjects, there will be no assessment of drug efficacy. Safety endpoints are briefly listed below. For a detailed schedule of activities, refer to Appendix A of the protocol. For a complete list of primary and secondary objectives and outcomes, refer to Section 3 of the SAP.

Safety will be assessed by the timing, frequency, relatedness to study drug, and severity of:

1. Treatment-emergent SAEs occurring from dosing through Final Visit (Day 8 ± 2), or ET
2. Clinical laboratory AEs occurring from dosing through Final Visit (Day 8 ± 2), or ET
3. Non-serious, unsolicited treatment-emergent AEs occurring from dosing through Final Visit (Day 8 ± 2), or ET.

Details of the study safety parameters can be found in the protocol.

5. SAMPLE SIZE CONSIDERATIONS

Since this is a pilot Phase 1, open-label trial with a single 4-g dose cohort of zoliflodacin, no formal sample size calculations based on testing a statistical hypothesis were constructed. Eight subjects will be enrolled, and it is planned to have seven evaluable subjects given zoliflodacin. This sample size will provide sufficient information to estimate exposure to the 4-g dose of zoliflodacin and to assess its safety.

6. GENERAL STATISTICAL CONSIDERATIONS

6.1. General Principles

Tabulations will be used extensively to summarize the data. Summary statistics for continuous data will include the mean, median, standard deviation, and range (minimum and maximum values). Summary statistics for discrete data will include counts and percentages, contingency tables, and associated confidence intervals (CIs). Denominators will be shown for all percentages (as N=X). When 95% CIs are given for a binary variable, Wilson Score CIs will be used. Parameters will be summarized overall and not by any subgroup.

In general, all data will be listed, sorted by subject ID, and when appropriate, by visit number within subject. The total population size relevant to specific tables or to columns or rows within tables will be displayed.

Listings of individual subject data include a Subject ID column. The subject identifiers assigned by site staff are replaced throughout this report with the SDTM variable USUBJID to protect the confidentiality of those who volunteered to participate in this protocol. USUBJID has been created as a composite of the 3-letter Electronic Data Capture (EDC) platform code followed by a numeric identifier assigned chronologically to enrolled subjects as well as screening failures across all sites and protocols in the EDC platform. Any data sharing activities will include the USUBJID and not the subject identifiers assigned at the site.

6.2. Timing of Analyses

The final analysis will be performed after database lock.

6.3. Analysis Populations

A tabular listing of all subjects, visits, and observations excluded from the analysis of PK data will be provided in the CSR ([Listing 4](#)).

6.3.1. Intention-to-Treat Analysis (ITT) Population

Not applicable.

6.3.2. Full Analysis Population

Not applicable.

6.3.3. Modified Intention-to-Treat (mITT) Population

Not applicable.

6.3.4. Evaluable Population

Not applicable.

6.3.5. Per Protocol Population

Not applicable.

6.3.6. Safety Population

All subjects who received the study drug will be included in the safety population and analyzed as treated.

6.3.7. PK Population

The PK analysis population will consist of all subjects who received zoliflodacin and have at least one quantifiable post-dosing drug concentration measured. The PK analysis subset will be based on the PK population, which includes all subjects who completed the PK part of the trial without any protocol violations that would likely affect the PK results and who have evaluable plasma concentration data for zoliflodacin from whom at least a subset of the designated PK parameters can be determined.

6.3.8. Immunogenicity Population

Not applicable.

6.4. Covariates and Subgroups

The protocol does not define any formal subgroup analyses, and the study is not adequately powered to perform subgroup analyses.

6.5. Missing Data

All attempts will be made to collect all data per protocol. Clinical labs will not be collected for Day -1 if collected ≤ 7 days of dosing. Therefore, missing clinical laboratory results on Day -1 only will be imputed using last observation carried forward when results with 7 days prior to dosing are available. Missing clinical laboratory results on Day 4 or "Day 4 or ET" will not be imputed. Missing pre-dose PK samples will have concentrations imputed as BQL (below quantification limit). No other imputation will be performed for missing values. Outliers will not be excluded from the primary analyses. Outliers identified during the PK analysis will be discussed in the analysis report.

6.6. Interim Analyses and Data Monitoring

There are no planned interim analyses for this study.

An SMC will review all the safety data to Day 8 or ET in the study cohort. If any of the predefined objective criteria for halting the study, listed in Section 9.5.1 of the protocol, are met, a SMC ad hoc meeting will be held to review all available safety data (see Section 9.6.2 of the protocol for more details).

6.7. Multicenter Studies

Not applicable. This is a single site study.

6.8. Multiple Comparisons/Multiplicity

This is a small Phase 1 first-in-human study with multiple primary endpoints. The primary endpoints are descriptive rather than hypothesis tests, no adjustments for multiple testing are planned.

7. STUDY SUBJECTS

7.1. Disposition of Subjects

Screened subjects who were ineligible for enrollment in the study will be summarized by inclusion and exclusion criteria in [Table 7](#), and enrolled subjects who were ineligible for inclusion in the analysis populations will be presented by reason for subject exclusion in [Table 6](#).

Subject disposition will be summarized ([Table 5](#)), showing the number of subjects who screened, enrolled, dosed, completed sample collection, and completed follow-up. Subjects who terminated early from the study will be listed ([Listing 1](#)). Subjects who were excluded from the PK population, then PK analysis subset, or safety population will be listed, including reason for exclusion ([Listing 4](#)).

7.2. Protocol Deviations

A summary of protocol deviations will be presented by the deviation category and reason in [Table 2](#). This table will provide both the number of subjects and the number of deviations for each category.

All subject-specific protocol deviations and non-subject-specific protocol deviations will be listed ([Listing 2](#) and [Listing 3](#), respectively).

8. EFFICACY EVALUATION

There are no efficacy endpoints for this trial

8.1. Primary Efficacy Analysis

Not applicable.

8.2. Secondary Efficacy Analyses

Not applicable.

8.3. Exploratory Efficacy Analyses

Not applicable.

9. SAFETY EVALUATION

All safety analyses will be presented using the safety population. When calculating the incidence of AEs (i.e., on a per subject basis), each subject will be counted once and any repetitions of AEs within a subject will be ignored for events coded in the same category by the Medical Dictionary for Regulatory Activities (MedDRA); the denominator will be the total safety population size. Moreover, events thus summarized will be coded to the highest severity observed per toxicity tables ([Table 3](#) and [Table 4](#)).

9.1. Demographic and Other Baseline Characteristics

Sex, ethnicity, and race of all subjects will be summarized ([Table 8](#)). Ethnicity will be categorized as “Hispanic or Latino,” or “Not Hispanic or Latino,” or “Unknown/Not Reported.” In accordance with NIH reporting policy, subjects may self-designate as belonging to more than one race or may refuse to identify a race, the latter reflected in the eCRF as “No” to each racial option. Age (in years), height (in m), weight (in kg), and BMI (in kg/m²) will be summarized ([Table 9](#)).

Individual subject listings will be presented for all demographic and baseline characteristics ([Listing 5](#)).

9.1.1. Prior and Concurrent Medical Conditions

Medical history (MH) including all current illnesses and past pre-existing medical conditions will be MedDRA coded using MedDRA dictionary version 20.1 or higher. Summaries of subjects’ pre-existing medical conditions by MedDRA system organ class (SOC) will be presented ([Table 10](#)). Individual subject listings including medical history term, condition start and end day, SOC, and PT will be presented for all medical conditions ([Listing 6](#)). Surgeries, and the underlying illness indicating the surgery, were collected as separate medical history terms, and will be reported as separate rows in the listing.

9.1.2. Prior and Concomitant Medications

All medications will be coded using the current version of the World Health Organization (WHO) Drug dictionary. The use of prior and concomitant medications taken during the study will be summarized by Anatomical Therapeutic Chemical (ATC) classification codes ATC 1 and ATC 2 (separately in [Table 117](#) for prior medications and [Table 118](#) for concomitant medications). Individual subject listings will be presented for all prior and concomitant medications (separately in [Listing 18](#) for prior medications and [Listing 19](#) for concomitant medications).

9.2. Measurements of Treatment Compliance

All subjects were to receive a single 4 g dose of zoliflodacin administered in the clinic. The dates and times of administration are listed for each subject in [Listing 7](#). Subjects unable to ingest the full amount of the initial [REDACTED] of study drug suspension or who vomit within 24 h after dosing will be withdrawn from the study and replaced (See Section 5.3.3 and 5.3.4 of the protocol). Subjects who do not ingest the content of the second [REDACTED] of study drug suspension will not be withdrawn from the study. Subjects who received any amount of the study drug but withdraw from the trial will be encouraged to continue follow-up (with subjects’ consent) for safety assessments and PK sample collection.

Subjects receiving the full initial [REDACTED] suspension and the full [REDACTED] wash ([REDACTED]) will be reported in [Listing 7](#) as receiving “4 g” of the drug. Subjects receiving an incomplete dose will be reported in [Listing 7](#) as receiving “<4 g” of the drug.

9.3. Adverse Events

When calculating the incidence of AEs within each category (i.e., on a per subject basis), each subject will only be counted once and any repetitions of AEs within a subject will be ignored; the denominator will be the total safety population size. When multiple AEs of different severities are observed for a subject within a category, the worst severity will be tabulated for calculations of incidence. All reported AEs will be included in the summaries and analyses.

9.3.1. Solicited Events and Symptoms

There are no solicited symptoms or AEs in this trial.

9.3.2. Unsolicited Adverse Events

The proportion of subjects reporting at least one unsolicited AE after dosing and prior to Day 8 or ET will be summarized by MedDRA SOC, higher level group term (HLGT), and preferred term (PT). A 95% Wilson Score CI will be presented for each MedDRA SOC, HLGT, and PT. Tables, figures, and listings of AEs will include clinical laboratory AEs and ECG AEs.

AEs by subject will be presented in [Listing 8](#). Additionally, moderate and severe non-serious AEs will be listed in [Table 15](#).

A brief overall summary of AEs will be given in [Table 11](#). The following summaries for unsolicited AEs will be presented by MedDRA SOC, HLGT, and PT:

- Frequency (number and percent of subjects with an AE of mild severity or greater, with 95% Wilson Score intervals) and number of AE, regardless of severity or relationship to study product ([Table 12](#))
- Frequency of AEs by severity and relationship to study product ([Table 13](#));
- Bar chart of frequency of related AEs by severity and MedDRA SOC ([Figure 2](#)). This figure describes the total number of occurrences of each AE, including multiple occurrences per subject.
- Bar chart of incidence of serious and non-serious AEs by maximum severity and MedDRA SOC ([Figure 1](#)). This figure describes the number and percent of subjects with an AE.

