9.2.1.3 Reporting Adverse Events

AEs will be captured on the appropriate subject's source document and eCRF. Information collected for AEs includes event description, time of onset, investigator assessment of severity, relationship to the study drug, date of resolution of the event, seriousness, and outcome.

All AEs will be documented from the time of drug dosing up to and including Final Visit. AEs will be followed to resolution or until considered stable in the clinical judgment of the study investigator. Evaluation of AEs may require unscheduled visits and clinical and laboratory investigations, according to the clinical judgment of the Site PI and study physicians.

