11.4.3 Safety Analysis Plan

11.4.3.1 Adverse and Serious Adverse Events

AEs will be coded using the latest version of the Medical Dictionary for Regulatory Activities[®] (MedDRA). All AEs occurring after study drug dosing will be summarized using frequency counts and percentages. The following summaries will be presented for AEs and SAEs:

- Overall (i.e., regardless of severity or relationship to treatment);
- By severity grade (mild, moderate, or severe);
- By relationship to study drug;
- By MedDRA level hierarchy (system organ class [SOC], higher level group term [HLGT], and preferred term [PT]).

Unless otherwise specified, at each level of subject summarization in reporting the incidence of AEs, a subject will be counted once if the subject reported one or more AEs. If more than one occurrence of an AE is reported, the AE of the worst severity or the worst-case relationship assessment will be summarized.

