3.2. Endpoints

Primary Endpoints:

- C_{max} , T_{max} , area under the curve (AUC) until last measurable concentration ($AUC_{(0-last)}$), and other PK parameters for zoliflodacin determined using plasma concentrations of zoliflodacin in blood samples collected on Day 1 [baseline (30 min before dosing) and 0.5 h, 1 h, 2 h, 3 h, 4 h, 6 h, 8 h, and 12 h after dosing], Day 2 [24 h and 36 h after dosing], Day 3 [48 h after dosing], and Day 4 [72 h after dosing], or early termination (ET), and measured using a validated high performance liquid chromatography tandem mass spectrometry (HPLC-MS/MS) method

Secondary Endpoints:

- The occurrence of treatment-emergent serious adverse events (SAEs) from administration of zoliflodacin on Day 1 to Final Visit (Day 8 ± 2), or ET
- The occurrence of unsolicited treatment-emergent adverse events (AEs) from administration of zoliflodacin on Day 1 to Final Visit (Day 8 ± 2), or ET
- The changes from baseline (up to 60 min before dosing) in vital signs (VS) following administration of zoliflodacin, as measured on Day 1 [1 h, 2 h, and 4 h after dosing], Days 2, 3, and 4 [24 h, 48 h, and 72 h, respectively, after dosing], and Final Visit (Day 8 ± 2), or ET
- The changes from baseline (Day -1) in clinical laboratory values following administration of zoliflodacin, as measured on Day 4, or ET
- The changes from baseline (up to 60 min before dosing) in electrocardiograph (ECG) parameters following administration of zoliflodacin, as measured on Day 1 [1 h, 2 h, and 4 h after dosing] and Day 4 [72 h after dosing], or ET

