9.7. Vital Signs and Physical Evaluations

VS measurements include systolic blood pressure, diastolic blood pressure, pulse rate, respiratory rate, and oral temperature. VS will be assessed within 60 min of dosing (baseline), 1 h (± 10 min), 2 h (± 10 min), and 4 h (± 10 min) after dosing, and at Day 2, Day 3, Day 4, and Day 8 or ET. VS will be tabulated by parameter, severity grading, and visit (Table 96, Table 97, Table 98, Table 99, Table 100, and Table 101) and listed (Listing 15). Additionally, descriptive statistics, including mean, standard deviation, median, minimum and maximum will be presented to summarize VS at baseline and post-dose and will also present change from baseline (Table 102, Table 103, Table 104, Table 105 and Table 106). For each vital sign, individual line plots showing the vital sign over time will be shown by parameter (Figure 28, Figure 29, Figure 30, Figure 31 and Figure 32). Subjects will not be labeled in the line plots, as the purpose of the figures is to give an overall trend of trajectory.

In tables of severity, maximum severity observed for the parameter after dosing will be summarized. Tables of maximum severity for “Any Parameter” will be included for VS results. In these tables, the maximum severity across all VS is summarized by visit, and from maximum severity post baseline. Ordinarily, only the maximum severity event will be counted in the summary tables. For instance, if subject has a mild decrease and a moderate increase observed post-dose, they will be counted once as a moderate increase for maximum severity post-baseline. In the exceptional case that a subject has an increase and a decrease of equal maximum severity, they will be counted twice for maximum severity post baseline, once for an increase and once for a decrease.

A complete physical examination (PE), except genital, rectal and breast exams, will be conducted at Screening and at Day 8 (± 2) or ET. This examination will assess general appearance, HEENT (head, eyes, ears, nose and throat), heart, lungs, abdomen, skin, musculoskeletal system, and lymph nodes, and include an abbreviated neurological exam. An abbreviated PE will be performed on Day -1 (unless a complete PE was performed < 7 days before dosing) and Day 4. An abbreviated PE differs from a complete PE in that the

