14.3.1.2 Unsolicited Adverse Events

Table 12: Summary of Unsolicited Adverse Events by MedDRA System Organ Class, Higher Level Group Term, and Preferred Term

MedDRA System Organ Class	MedDRA Higher Level Group Term	MedDRA Preferred Term	Any Time Post Dose (N=X)			
			n	%	95% CI	Events
Any SOC	Any HLGT	Any PT	x	xx	xx, xx	X
[SOC 1]	HLGT 1	[PT 1]				
		[PT 2]				
[SOC 2]	HLGT 2	[PT 1]				
		[PT 2]				

Table 13: Unsolicited Adverse Events by MedDRA System Organ Class, Higher Level Group Term, Preferred Term, Maximum Severity, and Relationship

MedDRA System Organ Class	MedDRA Higher Level Group Term	Preferred Term	Severity	All Subjects (N = X)			
				Related		Any Relatedness	
				n	%	n	%
Any SOC	Any HLGT	Any PT	Any Severity	x	x	x	x
			Mild	x	x	x	x
			Moderate	x	x	x	x
			Severe	x	x	x	x
SOC 1	Any HLGT	Any PT	Any Severity	x	x	x	x
			Mild	x	x	x	x
			Moderate	x	x	x	x
			Severe	x	x	x	x
SOC 2	HLGT 1	Any PT	Any Severity	x	x	x	x
			Mild	x	x	x	x
			Moderate	x	x	x	x
			Severe	x	x	x	x
SOC 3	HLGT 1	PT 1	Any Severity	x	x	x	x
			Mild	x	x	x	x
			Moderate	x	x	x	x
			Severe	x	x	x	x

Note: N = Number of subjects in the Safety Analysis Population.

[1] For severity, a subject is counted once per preferred term and is summarized according to their highest severity. Events are summarized separately for related events only and all AEs regardless of relatedness.

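### SAP 9.3.2 closes the unsolicited-AE window before Day 8 or ET, while the endpoint and the rest of the plan include the Final Visit and ET

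*SAP*

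**What the plan says.** SAP 9.3.2 (Unsolicited Adverse Events) states: "The proportion of subjects reporting at least one unsolicited AE after dosing and prior to Day 8 or ET will be summarized". The same paragraph attaches a 95% Wilson interval to each SOC, HLGT and PT, and says that the AE displays include laboratory and ECG AEs.

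Other parts of the plan set the window differently:

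- SAP 3.2 (Endpoints), secondary endpoint: "The occurrence of unsolicited treatment-emergent adverse events (AEs) from administration of zoliflodacin on Day 1 to Final Visit (Day 8 ± 2), or ET".
- SAP 4.5 (Efficacy and Safety Variables): "Non-serious, unsolicited treatment-emergent AEs occurring from dosing through Final Visit (Day 8 ± 2), or ET".
- SAP 9.3 (Adverse Events), the parent section: "All reported AEs will be included in the summaries and analyses".
- SAP Table 12 shell, whose column heading begins "Any Time Post Dose (N=X".
- Protocol 11.4.3.1: "All AEs occurring after study drug dosing will be summarized using frequency counts and percentages".
- Protocol 9.2.1.3, on collection: "All AEs will be documented from the time of drug dosing up to and including Final Visit".

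SAP section 15 declares no change to the planned analyses.

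**The concern.** The SAP gives two windows for one proportion. All the other statements reach the Final Visit or ET, or set no upper limit. Section 9.3.2 stops short of both. It is also the sentence that sets up the estimate with confidence intervals for a secondary endpoint, so two programmers working from the same data could fill Table 12 with different counts. The narrower reading can only remove events, so any error makes the 4-g dose look better tolerated.

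The excluded moments are assessment points. The Final Visit has a complete physical examination, vital signs and an AE review (protocol 7.5). The ET visit adds laboratory tests and an ECG (protocol 7.6). Scheduled post-dose laboratory tests are taken only on Day 4 or at ET (protocol 8.2.1.1), and a laboratory abnormality of Grade 1 or higher on the toxicity table is entered as an AE (protocol 9.2.4). For a dosed subject who terminates before Day 4, a window closing before ET would therefore drop AEs first found in that subject's only scheduled post-dose laboratory sample. The plan foresees early withdrawal after dosing, for example after vomiting within 24 h (protocol 5.3.4 and 6.5).

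**Working it through.** The plan gives no figure of its own to reproduce on this point. The check compares the texts and then sizes the difference.

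**Step 1: the windows side by side**

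| Source | End of window | Final Visit or ET included? |
|---|---|---|
| SAP 9.3.2 | before Day 8 or ET | no |
| SAP 3.2 | to Final Visit (Day 8 ± 2) or ET | yes, on the ordinary reading of 'to' |
| SAP 4.5 | through Final Visit (Day 8 ± 2) or ET | yes |
| SAP 9.3 | all reported AEs | yes |
| SAP Table 12 shell | any time after dosing | yes |
| Protocol 11.4.3.1 | all AEs after dosing | yes |
| Protocol 9.2.1.3 (collection) | up to and including Final Visit | yes |

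**Step 2: what 'Day 8' could mean**

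SAP 9.7 uses Day 8 as a visit label: "and at Day 2, Day 3, Day 4, and Day 8 or ET". The Final Visit may fall on Days 6 to 10 (8 − 2 to 8 + 2).

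*Calendar-day reading.* Days 1 to 7 count, so days lost = max(0, visit day − 7).

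| Final Visit on | Days lost |
|---|---|
| Day 6 | 0 |
| Day 7 | 0 |
| Day 8 | 1 |
| Day 9 | 2 |
| Day 10 | 3 |

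*Visit-label reading.* Nothing before the visit is lost, but AEs starting at the visit are. Protocol 9.2.1.3 collects time of onset. If a programmer compared dates only, the whole visit day would go, which is 1 day out of 6 to 10.

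Under either reading, AEs starting on the ET day are lost.

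**Step 3: effect on a table row**

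Inputs: 8 subjects planned (SAP 5) and up to 2 alternates (protocol 5). The safety population is everyone dosed (SAP 6.3.6), so N = 10 applies only if both alternates are also dosed. The event counts are assumed for illustration.

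One subject is worth 1/8 = 12.5 points, 1/9 = 11.1 points or 1/10 = 10.0 points.

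Wilson 95% interval, with z² = 3.8415:

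centre = (p + z²/2n) / (1 + z²/n)

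half-width = z·√[p(1 − p)/n + z²/4n²] / (1 + z²/n)

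- 1/8: centre = (0.125 + 0.2401)/1.4802 = 0.2467; half-width = 1.96 × √(0.01367 + 0.01501)/1.4802 = 0.2242; interval 2.2 to 47.1%.
- 0/8: lower limit 0; upper limit = 0.4802/1.4802; interval 0 to 32.4%.
- 1/10: 1.8 to 40.4%.
- 0/10: 0 to 27.8%.

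So at N = 8, a single first-in-category AE at the excluded boundary changes the row from 12.5% (2.2 to 47.1%) to 0% (0 to 32.4%).

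**The case against.** The strongest reply is that the SAP largely answers the question itself. The parent section and the Table 12 heading both include everything after dosing. The bullet that specifies Table 12 has no cut-off, and the sentence with the cut-off cites no table. 'Day 8 or ET' elsewhere in the SAP is shorthand for the last visit, and section 15 declares no change, so this is probably loose drafting. The calendar-day losses are then the less likely case. The Final Visit has no scheduled safety laboratory tests or ECG, so only examination, vital-sign or subject-reported onsets are exposed there. The trial is small and descriptive, and Listing 8 shows every AE.

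Much of this stands. The wording was probably not meant to narrow the analysis, and a careful programmer may follow the shell. It is an inference that the sentence governs Table 12, although Table 12 is the only AE shell with a confidence interval column. The effect requires a first-in-category onset at the boundary.

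Three points do not go away. Treating Day 8 as a visit label leaves the conflict in place, because the word 'prior' still excludes the visit. The limited assessments at the Final Visit do not help with ET, where laboratory tests and an ECG are taken. And having other passages that point the right way does not make it acceptable to keep an incompatible rule in the section that specifies the analysis.

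**Conclusion.** The concern holds. SAP 9.3.2 contradicts the endpoint it is meant to analyse, and no declared change explains the difference. Read literally, it loses AEs starting on the ET day under either reading, plus either onsets at the Final Visit (visit label) or up to 3 days of onsets (calendar day, Final Visit on Day 10).

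Each affected subject lowers a row by 12.5 points at N = 8, or 10.0 points at N = 10, always downward. This assumes that the cut-off is applied to onset and that the subject has no earlier AE in that category. If no AE starts at the boundary, the counts do not change.

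The consequence is confined to AE proportions and their intervals for a secondary endpoint. Listing 8 and Tables 14 and 15 state no cut-off and would still show the event. The primary PK endpoints are unaffected. The text should be corrected, but it does not threaten the trial's main result.

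**What to change.** In SAP 9.3.2, replace the phrase that ends the window before Day 8 or ET with: *from dosing through and including the Final Visit (Day 8 ± 2) or ET*. That puts the text behind Tables 11 to 13 on the window of SAP 3.2 and 4.5.

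SAP 6.6 can stay as it is: it describes safety data to Day 8 or ET, which does not exclude the end point.

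The cost is one phrase in the SAP, with no extra data and no change to the table shells.
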